16.3 Vital signs

The summary of vital signs will only include on treatment data, which are defined as those vital sign measurements after the first dose of study treatment and on or before last dose + 84 days.

Analysis in vital sign measurement using descriptive summary statistics for the change from baseline for each post-baseline visit in extension will be performed. These descriptive summaries will be presented by vital sign and treatment dose. Change from baseline will only be summarized for subjects with both baseline and post-baseline values and will be calculated as: change from baseline = post-baseline value – baseline value

The number and percentage of subjects with newly occurring notable vital signs will be presented. Criteria for notable vital sign abnormalities are provided in [Table 16-4](#) below.

Table 16-3 Criteria for notable vital sign abnormalities

Vital sign (unit)	Notable abnormalities
Systolic blood pressure (mmHg)	≥ 140 mmHg or < 90 mmHg
Diastolic blood pressure (mmHg)	≥ 90 mmHg or < 60 mmHg
Pulse (bpm)	> 100 bpm or < 60 bpm

16.4 Electrocardiogram (ECG)

The summary of ECG will only include on treatment data, which are defined as those ECG measurements after the first dose of study treatment and on or before last dose + 84 days.

The following quantitative variables will be summarized: ventricular rate, RR interval, PR interval, QRS duration, QT interval, and corrected QT interval (QTc). Both Bazett (QTcB) and Fridericia (QTcF) corrections will be presented for QTc.

QTc will generally be summarized by computing the number and percentage of subjects (including 95% CIs for pooled analyses, e.g. DMC or SCS) with:

- QTc > 500 msec
- QTc > 480 msec
- QTc > 450 msec
- QTc changes from baseline > 30 msec
- QTc changes from baseline > 60 msec
- PR > 250 msec

Summary statistics will be presented by visit and treatment dose in safety population.

Subjects with notable abnormal ECG parameters as described above, after baseline will be summarized.

Shift tables comparing baseline ECG interpretation (normal, abnormal, not available, total) with the worst on-study interpretation (normal, abnormal, not available, total), listing of all newly

occurring or worsening abnormalities, as well as a by-subject listing of all quantitative ECG parameters.

16.5 Immunogenicity

A listing of immunogenicity (anti-AIN457 antibodies) together with a listing with the impact of ADA development on the primary efficacy will be provided.

16.6 Compound specific safety evaluation

Safety topics of interest, such as risks defined in the Safety Profiling Plan, Risk Management Plan or topics of interest regarding signal detection or routine analysis are defined in the Program Case Retrieval Sheet that is stored in CREDI at the path *Cabinets/CREDI Projects/A/AIN457A/Integrated Medical Safety*.

The crude incidence and exposure-adjusted incidence rates will be summarized. In addition, listings will be provided presenting which subjects experienced which risk.

Important note: For the evaluation of SPP risks primary and secondary system organ classes of the MedDRA dictionary (latest version) will be considered.

17 Interim analyses

Interim analyses are planned in order to support regulatory filing and for purpose of publication after subjects complete additional years of treatment in this extension study. Additional analyses may be performed to support health authority interactions, as necessary.

18 Determination of sample size

It is estimated that approximately 75% to 85% of subjects enrolled in the core study will complete the entire treatment period and be eligible for entry into the extension study, which is equivalent to about 279 to 316 subjects.

19 Appendix

Group 1: [REDACTED], Cardiovascular panel,

Group 2: X-Ray

Group 3: Lipids

Group 4: weight

Group 5: ECG,

Group 6: Physical exam, Vital signs

Group 7: Hematology, Blood chemistry, Urinalysis, Patient's global assessment of disease activity, Patient's assessment of spinal pain, [REDACTED], [REDACTED]

[REDACTED], Urine pregnancy test

Group 8: [REDACTED]

* The first administration of study treatment (first dose in core) is defined as Day 1.

The following rules are used to determine the window for an applicable visit post baseline: “Lower limit” = “upper limit of prior applicable visit” + 1. “Upper limit” = “target of current visit” + integer part of (“target of next applicable visit” – “target of current visit”)/2. Lower limit of the first applicable visit is always 2.

The mapping described above applies to all core visits (not just scheduled visits). Repeat and/or unscheduled visits (which will be numbered in the database according to new NCDS standards) will be mapped for analysis purposes in the same way as scheduled visits. This leaves the possibility, then, for multiple measurements within an analysis window. The following conventions will be used to determine the appropriate measurement to be summarized in the event of multiple measurements within a visit window.

Table 19-2 Rules for flagging variables

Timing of measurement	Type of data	Rule
Baseline	All data	The last measurement made prior to administration of the first dose of study treatment – note this may include measurements taken on the day of randomization (e.g. lab). Baseline assessments scheduled for and captured on Day 1 will be considered baseline measurements regardless of the time of assessment. If a patient did not receive any dose of study treatment then the randomization date will be used.
Post-baseline efficacy during the core study phase	All data	
For visits without switch of treatment in the window, the measurement closest to the target will be used. In the event two measurements are taken equally apart (e.g. 1 before target date and 1 after) the first one will be used.
Post-baseline safety during the core study phase	Summary visit information (e.g. lab, ECG, etc.)	
For visits without switch of treatment in the window, the measurement closest to the target will be used. In the event two measurements are taken equally apart (e.g. 1 before target date and 1 after) the first one will be used.
Post-baseline safety during the core study phase	Notable abnormalities (e.g. lab)	The most extreme measurement in the window will be used. Note this means a patient can have a notably high and notably low measurement within a window.

No visit windows were used in case of up-titration. The before up-titration measurement is considered as the last visit measurement, performed on or before the date that patient took the up-titration dose. The up-titration data analysis will be based on week intervals; it is accounting for the time period between the actual date of exposure to the up-titrated dose and the last visit date of the subject:

- 4 – 8 weeks after up-titration
- 12 – 20 weeks after up-titration
- 24 – 32 weeks after up-titration
- 36 – 44 weeks after up-titration
- 48 – 60 weeks after up-titration

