5.5.5 Permitted dose adjustments and interruptions of study treatment

Study treatment dose adjustments are not permitted until approval and implementation of Protocol Amendment 1. After approval and implementation of the Protocol Amendment 1, the

study medication for subjects on the 75 mg treatment arm should be escalated from 75 mg s.c. to 150 mg s.c. every 4 weeks for patients whose overall therapeutic response is not fully achieved with the current dose of 75 mg and may improve with a higher dose, as judged by the investigator. The escalation of the study medication may be determined at any site visit. For patients escalated to 150 mg, no dose reduction can be performed at a later time point.

Study treatment interruption is permitted only if, in the opinion of the investigator, a subject is deemed to be placed at a significant safety risk unless dosing is temporarily interrupted. In such cases, study treatment should be interrupted only during the time that this risk is present and ongoing. Study treatment can be restarted at the next scheduled visit after resolution of the safety risk.

The effect of secukinumab on live vaccines is unknown; therefore live vaccines should not be administered during participation in the study. In case a live vaccine has been administered due to a medical urgency, study treatment should be interrupted for 12 weeks.

These changes must be recorded on the Dosage Administration Record CRF.

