Administration of study treatment ⁴	X	X	X	X	X	X	X	X	X	X	X	X	X	X
Conc. Medication/non-drug therapy	Update as necessary													
Adverse events/SAE ⁵	Update as necessary													
Patient's global assessment of disease activity (VAS)				X			X			X				X
Patient's assessment of Spinal pain (VAS)				X			X			X				X

[REDACTED]

Epoch	Treatment period 3													
Week (relative to baseline of phase III study)	104E1 ¹	108E1	112E1	116	120	124	128	132	136	140	144	148	152	156 ⁹ *
Lipids ⁸								X						X
Cardiovascular panel														X
Treatment period 3 completion form														X

¹ This visit corresponds to the Week 104 visit of the core study. Only those assessments which are unique to the extension study are mentioned here and the assessment carried out as part of Week 104 of the core study are not mentioned; however, those assessments need to be carried out as per core study protocol.

² Optional visits – Week 120, 124, 132, 136, 144, 148, 152. At these optional visits only those subjects who are unable to self-administer the PFS injections at home will visit the site and site staff will supervise self-administration or administer the PFS injection for them. Other subjects who can self-administer the PFS injection can do so at home at these optional visits.

³ These assessments are source documentation only and will not be entered into the eCRF

⁴ The study treatment (PFS) has to be administered every 4 weeks. From Week 104E1 to 116, subjects will visit the site every 4 weeks for administering the PFS injection (by self or by site staff). After Week 116, at visits marked as optional visits, subjects can self-administer the study PFS at home or may visit the site to receive the PFS administration by site staff.

⁵ AEs/SAEs occurring after the subject has signed the informed consent must be captured on the appropriate eCRF page.

[REDACTED]

[REDACTED]

⁸ Sample must be obtained fasting.

⁹ Site staff and subjects will be unblinded. Subjects will no longer receive placebo PFS after unblinding.

[REDACTED]

Epoch	Treatment period 3													
Week (relative to baseline of phase III study)	104E1 ¹	108E1	112E1	116	120	124	128	132	136	140	144	148	152	156 ^{9*}

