* For all subjects who discontinue or withdraw from the study, the investigator should ensure that the subject completes an end of treatment visit (corresponding to the last visit for the subject's current period of treatment) 4 weeks after last study treatment and also return after an additional 8 weeks for a final follow-up, F268 (12 weeks after last study treatment). The final visit should be performed before any new treatment is initiated.

Table 6-2 Assessment schedule - Part 2: Week 160 to Week 208

Epoch	Treatment period 4												
Week	160	164	168	172	176	180	184	188	192	196	200	204	208*
Optional Site Visit ¹	X	X		X	X		X	X		X	X	X	
Physical exam ²			X			X			X				X
Weight						X							X
Vital signs			X			X			X				X
Hematology, blood chemistry, urinalysis			X			X			X				X
Urine pregnancy test			X			X			X				X
ECG						X							X
Administration of study treatment ³	X	X	X	X	X	X	X	X	X	X	X	X	X
Conc. Medication/non-drug therapy	Update as necessary												
Adverse events/SAE ⁴	Update as necessary												
Patient's global assessment of disease activity (VAS)			X			X			X				X
Patient's assessment of spinal pain (VAS)			X			X			X				X

Epoch	Treatment period 4												
Week	160	164	168	172	176	180	184	188	192	196	200	204	208*
Lipids ⁶							X						X
Cardiovascular panel													X
Treatment period 4 completion form													X

¹ Optional visits – Week 160, 164, 172, 176, 184, 188, 196, 200, 204. At these optional visits only those subjects who are unable to self-administer the PFS injections at home will visit the site and site staff will supervise self-administration or administer the PFS injection for them. Other subjects who can self-administer the PFS injection can do so at home at these optional visits.

² These assessments are source documentation only and will not be entered into the eCRF

³ The study treatment (PFS) has to be administered every 4 weeks. From Week 104E1 to 116, subjects will visit the site every 4 weeks for administering the PFS injection (by self or by site staff). After Week 116, at visits marked as optional visits, subjects can self-administer the study PFS at home or may visit the site to receive the PFS administration by site staff.

⁴ AEs/SAEs occurring after the subject has signed the informed consent must be captured on the appropriate eCRF page.

⁶ Sample must be obtained fasting.

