14.1 Efficacy variables

Secondary [REDACTED] variables include:

- the proportion of subjects achieving ASAS40

For binary variables, the proportion of responders along with the 95% CI will be presented by groups according to the treatment sequence over analysis visits. For continuous variables, the change from core baseline will be summarized.

Results will be presented for the FAS, as well as subgroups by TNF α status (naive or IR) for the following variables: ASAS40, [REDACTED]

Graphical representation (line plots) regarding the response over time for the following measures will be provided in the observed data: ASAS20/40, [REDACTED]

[REDACTED] will also be graphically illustrated. The above mentioned figures will show the originally randomized AIN457 treatment groups.

Cumulative probability plots will be employed to display the change from baseline to week 208 illustrating the progression of subjects after 4 years [REDACTED]

Additional figures as in line plots, illustrating the up-titration effect of treatment will be created for the following parameters: ASAS20/40, [REDACTED]

ASAS20

The ASAS Response Criteria (ASAS20) is defined as an improvement of $\geq 20\%$ and ≥ 1 unit on a scale of 10 in at least three of the four main domains and no worsening of $\geq 20\%$ and ≥ 1 unit on a scale of 10 in the remaining domain.

The percentage of subjects experiencing ASAS20 response, followed by the respective 95% CI, will be presented by treatment sequence up to week 260 based on the observed data. The respective summaries will also be provided by TNF- α IR status.

Additional analysis will be based on the imputed responses only for the AIN457 150 mg group.

The percentage of subjects (and the 95% CI) experiencing ASAS20 response after up-titration will be presented in separate tables (observed data). Patients who had at least 1 dose of the up-titrated dose will be included.

[figure not shown]
ASAS40

[figure not shown]
The ASAS 40 response is defined as an improvement of $\geq 40\%$ and ≥ 2 units on a scale of 10 in at least three of the four main domains and no worsening at all in the remaining domain.

[figure not shown]
[figure not shown]
The percentage of subjects experiencing ASAS40 response, followed by the respective 95% CI will be presented by treatment sequence up to week 260 based on the observed data. The respective summaries will also be provided by TNF- α IR status.

[figure not shown]

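### The 4-8 week point after up-titration draws mainly on first higher doses taken between efficacy visits, so the displayed up-titration effect mixes change in response with change in who is counted

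*SAP*

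**What the plan says.** **Analysis.** SAP 14.1 plans separate observed-data tables of the percentage with ASAS20 and ASAS40 response after up-titration, for everyone who received the higher dose at least once. It also plans line plots "illustrating the up-titration effect of treatment will be created for the following parameters: ASAS20/40". SAP 19.1 gives the timing rules. No visit windows are used, and "The up-titration data analysis will be based on week intervals", which cover the "time period between the actual date of exposure to the up-titrated dose and the last visit date of the subject". The first interval is "4 – 8 weeks after up-titration"; the others are 12-20, 24-32, 36-44 and 48-60 weeks. The reference is defined thus: "The before up-titration measurement is considered as the last visit measurement, performed on or before the date that patient took the up-titration dose". No maximum age is set for it, and nothing requires the same subjects to appear in the reference and in an interval.

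**Conduct.** Protocol 5.5.5: "The escalation of the study medication may be determined at any site visit". Footnotes to Protocol Tables 6-1 to 6-3: "The study treatment (PFS) has to be administered every 4 weeks". In those tables, patient global assessment and spinal pain are marked only at Weeks 116, 128, 140, 156, 168, 180, 192, 208, 220, 232, 244 and 260. Between these lie 25 optional dosing visits with no efficacy assessment. The table footnotes say of them: "At these optional visits only those subjects who are unable to self-administer the PFS injections at home will visit the site".

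**The concern.** The first interval is shorter than the gap between efficacy visits. A subject who takes the first 150 mg dose at an efficacy visit has a same-day reference but is next assessed after that interval has closed. A subject who takes it between efficacy visits can supply a 4-8 week value, but the reference then dates from an earlier visit and may not describe the state that prompted escalation.

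The up-titration tables and plots are the only efficacy display described in the SAP that is aligned to the escalation date, and escalation is the main change made by Amendment 1. A reader will naturally take the first point after the dose as early onset, or as an early dip. If different subjects stand behind successive points, part of any rise or fall is a change of composition, and the planned output gives no means of separating the two.

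**Working it through.** **1. Confirm the efficacy grid.** SAP 19.1 gives the rule for Table 19-1: upper limit = target day + integer part of (next target - target)/2, and lower limit = previous upper limit + 1. With target day = 7 × week + 1 and the visits above preceded by Week 104:

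- Week 116: 813 + (897 - 813)/2 = 813 + 42 = 855. Table, Group 7: 855.
- Week 140: 981 + (1093 - 981)/2 = 981 + 56 = 1037. Table, Group 7: 1037.

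All 12 Group 7 upper limits from Week 104E1 to Week 244 are reproduced, and all 11 linked lower limits. Group 7 holds the global assessment and spinal pain, so the SAP uses the same grid as the protocol tables. Redacted rows cannot add ASAS time points: response needs improvement in three of the four main domains, and without global assessment and pain at most two are available.

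**2. Enumerate first-dose weeks.** Dosing weeks 116 to 256 in steps of 4: (256 - 116)/4 + 1 = 36, of which 11 are efficacy visits and 25 optional. For a first 150 mg dose at week w, age of before-value = w - last efficacy week ≤ w, and each later efficacy week e falls e - w weeks after the dose.

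| First 150 mg dose taken at | Weeks | Next scheduled assessment | Fills 4-8 | Age of before-value | Fills 12-20 |
|---|---|---|---|---|---|
| Efficacy visit, 116 to 244 | 11 | 12 weeks; 16 from Weeks 140, 192, 244 | 0 | 0 | 11 |
| Optional visit | 25 | 4 weeks (11), 8 weeks (11), 12 weeks (3) | 22 | 4, 8 or 12 weeks | 20 |
| All | 36 | | 22 | | 31 |

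- The three optional weeks that miss 4-8 weeks are 144, 196 and 248.
- Among the 22 that fill it, the before-value is 4 weeks old at 8 weeks, 8 weeks old at 11, and 12 weeks old at 3 (Weeks 152, 204, 256).
- The five weeks that miss 12-20 are 132, 184, 236, 252 and 256. All five fill 4-8, so 22 - 5 = 17 dose weeks fill both.
- At 0 of 36 weeks does the schedule give both a same-day before-value and a 4-8 week value.

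**3. Other routes into 4-8 weeks.**

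- Discontinuers have an end-of-treatment visit with the period-end assessments 4 weeks after the last dose (asterisk note, Tables 6-1 to 6-3). A subject up-titrated at an efficacy visit whose last dose is that one or the next is assessed 0 + 4 = 4 or 4 + 4 = 8 weeks after up-titration.
- Weeks 108E1 and 112E1 are on-site dosing visits, not optional. They reach Week 116 after 8 and 4 weeks, with before-values 4 and 8 weeks old. They count only if Amendment 1 was in force at the site by then; no date is given.
- The SAP clock starts at the dose. If the decision is made at an efficacy visit and the higher dose is first taken 4 weeks later, the subject is in the optional-visit row.

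**4. Share of the subset.** The documents do not say when subjects escalate. If first doses were spread evenly over the 36 weeks, 22/36 = 61% could supply a 4-8 week value. If 70-90% were taken at efficacy visits (an assumption), at most 10-30% could, early discontinuers aside.

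**The case against.** The case on the other side has force, and several stronger readings fail.

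- **That the interval is empty for every subject dosed at an efficacy visit, or fed only by optional visits.** A reader might infer this, but the three routes in step 3 rule it out. The end-of-treatment route admits subjects who stopped soon after up-titration, a selected group, so it does not improve comparability.
- **That the points rest on disjoint groups.** They do not. Contributors at 4-8 weeks belong to the up-titration subset, and 17 of the 22 dose weeks also fill 12-20. Real within-subject change is present in the curve; it is mixed with composition, not replaced by it.
- **That only subjects unable to self-inject attend optional visits.** The table footnotes say so, but Protocol 3.1 and the domiciliary paragraph of 5.5.4 let capable subjects choose to attend. Attendance is self-selected, not confined to one type of subject.
- **That the old before-value distorts the response rates.** ASAS response is judged against the core baseline, so the rate in an interval does not use the before-value. SAP 14.1 does not say how the line plots use it. Reading it as the starting point of the plot is an inference, though SAP 19.1 gives it no other stated purpose.
- **That the consequence is small.** The analysis is descriptive, without hypothesis tests, and each percentage carries a 95% CI. This stands, and it limits the severity. But a wide interval shows that n is small; it does not show that the subjects differ from those at the neighbouring point.

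Unscheduled assessments are not a planned remedy: SAP 19.1 restricts the extension analysis to nominal visits.

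**Conclusion.** The concern holds in limited form. For subjects on schedule and on treatment, a first 150 mg dose at an efficacy visit gives no 4-8 week assessment (0 of 11 weeks). The point rests mainly on doses at non-efficacy visits (22 of 25 optional weeks, and possibly Weeks 108E1 and 112E1), with before-values 4 to 12 weeks old, and on some early discontinuers. The 12-20 week interval is filled from 31 of 36 weeks. The set of subjects therefore shifts between successive points, and the displayed effect combines change in response with change in composition.

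The schedule result rests on 4-weekly dosing, on visits near their nominal weeks, and on timing counted from the dose, as SAP 19.1 has it. How many subjects are affected cannot be derived from the documents. The primary ASAS20 summary by treatment sequence does not use these intervals. This is a cheap improvement, not a flaw in the main analysis.

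**What to change.** In SAP 14.1 and 19.1:

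1. Keep all five intervals.
2. In each interval, show the before-value response and the after-value response for the same subjects (those with both), with n.
3. Report the age of the before-value in each interval, for example its median and range.
4. Do not join intervals containing different subjects as a single onset curve unless that paired reference is shown with it.

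Moving 4-8 weeks to a listing is not needed once the display is paired, and it would lose information. For first doses at Weeks 132, 184 and 236 the interval holds the first scheduled post-escalation value, and for Weeks 252 and 256 the only one.

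The cost is SAP wording and a same-subject restriction in the up-titration tables and plots. No new data are needed and treatment is unaffected. The downside is a slightly more complex output and a possibly small n, openly shown, at 4-8 weeks.
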